##### **4.2.2. Adherence to Study Drug**

The total number of tablets administered will be summarized using descriptive statistics.

The presumed total number of tablets administered to a subject will be determined by the data collected on the drug accountability eCRF using the following formula:

$$\text{Total Number of Tablets Administered} = \left( \sum \text{No. of Tablets Dispensed} \right) - \left( \sum \text{No. of Tablets Returned} \right)$$

If a bottle is dispensed and the bottle is returned empty, then the number of tablets returned will be entered as zero. If a bottle is dispensed but not returned (missing), it will be assumed that a subject did not take all study drugs as prescribed during the period for which the bottle is dispensed.

The level of prescribed adherence to the study drug regimen will be determined by the total amount of study drug administered relative to the total amount of study drug specified by the protocol for a subject who completes treatment in the study.

The level of prescribed adherence will be expressed as a percentage using the following formula:

$$\text{Prescribed Adherence (\%)} = \left( \frac{\text{Total Amount of Study Drug Administered}}{\text{Total Amount of Study Drug Specified by Protocol}} \right) \times 100$$

Descriptive statistics for adherence (sample size, mean, SD, median, Q1, Q3, minimum, and maximum) along with the number and percentage of subjects belonging to adherence categories (eg, < 75%, ≥ 75% to < 85% and ≥ 85%) will be provided by treatment group for the Safety Analysis Set.

No formal statistical testing is planned.

A by-subject listing of study drug administration and drug accountability will be provided by subject ID number in ascending order and visit in chronological order.

#### **4.3. Protocol Deviations**

Subjects who did not meet the eligibility criteria for study entry, but enrolled in the study will be summarized regardless of whether they were exempted by the sponsor or not. The summary will present the number and percentage of subjects who did not meet at least 1 eligibility criterion and the number of subjects who did not meet specific entry criteria by treatment group based on the All Randomized Analysis Set. A by-subject listing will be provided for those subjects who did not meet at least 1 inclusion or exclusion criterion. The listing will present the eligibility criterion (or criteria if more than 1 deviation) that subjects did not meet and related comments, if collected.

Protocol deviations occurring after subjects entered the study are documented during routine monitoring. The number and percentage of subjects with important protocol deviations by deviation reason (eg, nonadherence to study drug, violation of selected inclusion/exclusion criteria) will be summarized by treatment group for the All Randomized Analysis Set. A by-subject listing will be provided for those subjects with any protocol deviation.

## **5. BASELINE CHARACTERISTICS**

### **5.1. Demographics**

Subject demographic variables (ie, age, sex, race, and ethnicity) will be summarized by treatment group and overall using descriptive statistics for age, and using number and percentage of subjects for sex, race, and ethnicity. The summary of demographic data will be provided for the Safety Analysis Set.

In addition, a similar summary table will be provided by the consent status of participation in the Extended Viral Load Monitoring (yes or no).

A by-subject demographic listing, including the informed consent date, will be provided by subject ID number in ascending order.

### **5.2. Other Baseline Characteristics**

Other baseline characteristics include:

- Height (cm)
- Weight (kg)
- Body mass index (BMI; in  $\text{kg}/\text{m}^2$ )
- RSV types (RSV A or RSV B)
- Vital signs (pulse rate, systolic and diastolic blood pressure, body temperature, and respiratory rate)
- Smoking history
- Viral load
- Detectable RSV in nasal swab samples
- Co-pathogen types
- Duration of respiratory symptoms prior to the first dosing date
- FLU-PRO score
- FEV1 actual value (L)
- FEV1% predicted value

- FVC actual value (L)
- FVC% predicted value
- Stratification factors
- Hospitalization
- Have a new prescription for home oxygen therapy (yes or no)

These baseline characteristics will be summarized by treatment groups and overall using descriptive statistics (n, mean, SD, median, Q1, Q3, minimum, and maximum) for continuous variables and using number and percentage of subjects for categorical variables. In addition, baseline characteristics will be summarized by the consent status of participation in the Extended Viral Load Monitoring (yes or no) in a separate table. The summary of baseline characteristics will be provided for the Safety Analysis Set. No formal statistical testing is planned.

A by-subject listing of the baseline characteristics will be provided by subject ID number in ascending order.

### **5.3. Medical History**

Medical history will be collected at screening for disease-specific and general conditions (ie, conditions not specific to the disease being studied).

Lung transplant specific medical history (eg, transplant types, presence of chronic lung allograft dysfunction [CLAD], presence of bronchiolitis obliterans syndrome [BOS], BOS grade, and cytomegalovirus [CMV] status, and time from transplant to the first dosing date) will be summarized by treatment group and overall using descriptive statistics (n, mean, SD, median, Q1, Q3, minimum, and maximum) for continuous variables and using the numbers and percentages of subjects for categorical variables with each prepopulated condition. A summary of lung transplant specific medical history will be provided for the Safety Analysis Set. No formal statistical testing is planned.

General medical history will not be coded, but will be listed only.

## 6. EFFICACY ANALYSES

### 6.1. Primary Efficacy Endpoints

#### 6.1.1. Definition of the Co-Primary Efficacy Endpoints

The co-primary efficacy endpoints of this study are: the time-weighted average change in nasal RSV viral load ( $\log_{10}$  copies/mL) from Day 1/Baseline through Day 7 in the overall FAS population and in the subgroup population (defined as subjects in the FAS with duration of RSV symptoms prior to first dose of study medication  $\leq$  a median value of the distribution of RSV symptom duration in the overall FAS population).

The time-weighted average change in nasal RSV viral load ( $\log_{10}$  copies/mL) from Baseline (Day 1) to Day 7 as measured by RT-qPCR is defined as:

$$\frac{\sum_{i=a}^{b-1} \{0.5 \times (Y_i + Y_{i+1}) \times (t_{i+1} - t_i)\}}{(t_b - t_a)}$$

where  $Y_i$  is the change from Baseline in RSV  $\log_{10}$  viral load at Visit  $i$ ,  $t$  is the time at the specified timepoint (the actual study day),  $a$  is the baseline assessment at Day 1, and  $b$  is the last assessment at or prior to Day 7 visit.

The time-weighted average change, often referred to as the DAVG, provides the average viral burden change from baseline.

#### 6.1.2. Analysis for the Co-Primary Efficacy Endpoints

The co-primary analyses will test the 2 null hypotheses in the following sequence:

- $H_{01}$ : There is no difference between presatovir and placebo in the time-weighted average change in RSV  $\log_{10}$  viral load from Day 1 to Day 7 in the FAS
- $H_{02}$ : There is no difference between presatovir and placebo in the time-weighted average change in RSV  $\log_{10}$  viral load from Day 1 to Day 7 in the FAS with whose duration of RSV symptoms prior to the first dosing date of study medication is  $\leq$  median of the symptom duration distribution in the overall FAS population

To test the null hypothesis above, a parametric analysis of covariance (ANCOVA) model with corresponding baseline viral load and stratification factors (treatment of RSV infection with ribavirin and use of palivizumab or IVIG) as covariates will be used, at a 2-sided 0.05 level. Adjusted means and 95% confidence intervals (CIs) will be provided. The stratified Wilcoxon rank sum test will be implemented as a sensitivity analysis. The tests will be 2-sided with significance levels specified in Section 3.5.

Viral load values below the limit of detection (LOD) will be assigned as 0 if it is reported in the form of 'not detected'. A value of 1 unit less than the LOQ will be used for analysis if the viral load is reported in the form of "< x" (where x is considered the LOQ). Viral load data will be transformed using the base 10 logarithm for the analyses and summaries. To account for 0 values, 1 will be added to each viral load measurement before being transformed.

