4.2. Inclusion Criteria

Subjects must meet *all* of the following inclusion criteria at the time of randomization to be eligible for participation in this study:

- 1) Males and females ≥ 18 years of age who have received a LT (single or double) or heart/lung transplant > 90 days prior to Screening
- 2) Confirmed to be RSV-positive by local polymerase chain reaction (PCR) testing (starting from when the upper or lower respiratory tract sample is obtained) ≤ 7 days prior to IMP administration on Day 1/Baseline
- 3) New onset or acute worsening, if the symptom is chronic, of at least 1 of the following respiratory symptoms ≤ 7 days prior to IMP administration on Day 1/Baseline: nasal congestion, earache, runny nose, cough, sore throat, shortness of breath, or wheezing
- 4) An informed consent document signed and dated by the subject
- 5) A negative local urine or serum pregnancy test for female subjects of childbearing potential at Screening within 1 day prior to IMP administration. When available, existing local pregnancy test results obtained prior to Screening may be used, provided the testing was completed within 1 day prior to IMP administration.
- 6) Agreement from male and female subjects of childbearing potential who engage in heterosexual intercourse to use protocol specified method(s) of contraception as described in [Appendix 6](#)
- 7) Ability and willingness to complete necessary study procedures

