8.5. Efficacy Analysis

8.5.1. Primary Analysis

The primary endpoint is the time-weighted average change in nasal RSV viral load (\log_{10} copies/mL) from Day 1/Baseline through Day 7. The primary analysis will be performed on subjects included in the FAS and subjects included in the FAS with \leq median duration of symptoms prior to the first dose of study medication. To test these two co-primary null hypotheses of no difference between the presatovir and placebo treatment groups in the time-weighted average change in RSV viral load in the FAS and in the subgroup, parametric analysis of covariance (ANCOVA) models with corresponding baseline RSV viral load as a continuous variable and stratification factors included as covariates will be used. Adjusted means and 95% CIs will be provided. If stratification leads to small cell sizes, a modification to the stratification, which will be described in the SAP, will be implemented.

The co-primary analyses will be controlled at an overall type I error rate at the 2-sided 0.05 level in which the alpha level for the overall FAS population will be 0.04 and the alpha level for the subgroup population (subjects in the FAS with duration of RSV symptoms prior to first dose of study medication \leq median) will be 0.017, as determined by a grid search accounting for the known correlation of the populations.

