##### **3.1.2. Full Analysis Set**

The Full Analysis Set (FAS) includes all randomized subjects who took at least 1 full dose of study drug, and have an RSV viral load greater than or equal to the lower limit of quantification (LLOQ) of the RT-qPCR assay in the Day 1/Baseline nasal sample, as determined by RT-qPCR at the central lab. The subgroup analysis set includes subjects in the FAS who have the duration of RSV symptoms prior to the date of the first dose of study medication  $\leq$  a median value of the distribution of the duration of RSV symptoms in the overall FAS population. The FAS and the subgroup analysis set will be used as the primary analysis sets for efficacy analyses.

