### 3.3. Strata and Covariates

Subjects will be randomly assigned to treatment groups via the interactive web response system (IWRS) in a 2:1 ratio using a stratified randomization schedule. Stratification will be based on the following parameters:

- Treatment of RSV infection (yes or no) with ribavirin (oral, intravenous, or aerosolized)
- Use of palivizumab or IVIG (yes or no)

If there are discrepancies in stratification factor values between the IWRS and the clinical database, the values recorded in the clinical database will be used for analyses.

Efficacy endpoints will be evaluated using stratification factors as covariates for analyses, as specified in Section 6. If there are a small number of subjects (eg,  $\leq 4$  subjects) within a stratum of the stratification factor, then the stratum will be collapsed with the adjacent stratum for the analysis.

For efficacy endpoints, the baseline value of the efficacy variables will be included as a covariate in the efficacy analysis model.

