## Appendix 2. Alpha Allocation Approach

There are 2 test statistics in the study design, denoted by  $Z_k$  for  $k$ th population (1 = overall; 2 = subgroup population [including subjects who are in the FAS whose duration of RSV symptoms prior to the first dose of study medication is  $\leq$  median of the distribution of duration of RSV symptoms in the overall FAS population] with prevalence  $b_1$ ). Specifically,  $b_1 = 0.5$  for 50th percentile threshold.

For alpha spending across the 2 tests for the primary endpoint of time-weighted average change in viral load from baseline to Day 7, the following rules are implemented, where  $c_k$  denotes the rejection boundary for the  $k$ th population:

- Pre-fix rejection boundaries ( $c_1 = 2.054$ ) for the final analysis in the overall population

$\tilde{Z} = (Z_1, Z_2)$  is a vector of standardized test statistics that follow a multivariate normal distribution with mean  $\tilde{\mu} = (\mu_1, \mu_2)$ . For a very large clinical trial and assuming no prognostic or predictive effect of duration of RSV symptoms prior to the first dose on the primary endpoint, the variance-covariance matrix for the vector  $\tilde{Z}$  can be shown to be:

$$\Sigma = \begin{pmatrix} 1 & \sqrt{b_1} \\ \sqrt{b_1} & 1 \end{pmatrix}$$

Under the null hypothesis,  $\tilde{\mu} = (0, 0)$ . Given the above rules and the variance-covariance matrix  $\Sigma$ , the table below presents the rejection boundaries for the final analysis, which can be numerically calculated such that the overall type I error rate is maintained at the 2-sided 0.05 level.

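### The primary ANCOVA leaves out pre-treatment symptom duration; adding it to the FAS model costs almost nothing and would help if duration predicts DAVG7 beyond baseline viral load

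*SAP*

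**What the plan says.** SAP 6.1.2 tests both co-primary hypotheses, H01 in the FAS and H02 in the short-duration subgroup, with an ANCOVA "with corresponding baseline viral load and stratification factors (treatment of RSV infection with ribavirin and use of palivizumab or IVIG) as covariates". Protocol 8.5.1 names the same model, "with corresponding baseline RSV viral load as a continuous variable and stratification factors included as covariates will be used". The general rule in SAP 3.3 goes no further: "For efficacy endpoints, the baseline value of the efficacy variables will be included as a covariate in the efficacy analysis model". The two stratification factors are ribavirin treatment and palivizumab or IVIG use, so randomization does not balance symptom duration.

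Duration nevertheless defines a primary population. SAP 3.1.2 states: "The subgroup analysis set includes subjects in the FAS who have the duration of RSV symptoms prior to the date of the first dose", with the cut at the FAS median. It is also among the baseline characteristics summarized by arm in SAP 5.2: "Duration of respiratory symptoms prior to the first dosing date".

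The primary sensitivity analyses in SAP 6.1.2 and 6.1.3 are a stratified Wilcoxon test, the per-protocol set, and FAS subjects with a post-baseline swab. None is described as adjusting for duration. The exploratory sections are redacted, so an adjusted analysis there cannot be ruled out, but it would not alter the primary model.

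**The concern.** A baseline variable that may predict the outcome, has a value for each subject classified by the median split, and is not balanced by stratification is a natural covariate in a trial of 51 evaluable subjects. The documents give some reason to think duration could be prognostic. Protocol 1.1 and 1.4 qualify the shedding times seen in earlier lung-transplant trials by noting how long after onset those patients were enrolled.

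Two things are at stake. If duration explains part of the DAVG7 variation left after baseline viral load and the strata, leaving it out makes the confidence interval wider than it need be. And if the arms happen to differ in time since onset, the FAS estimate moves with that difference. The plan would then have no pre-specified adjusted result, and an adjustment chosen after unblinding would carry less weight.

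**Working it through.** **Inputs.** From SAP 1.3: SD 1.2; 34 vs 17 and a 1.2 log difference in the FAS; 17 vs 9 and a 1.5 log difference in the subgroup. From SAP 3.5: two-sided alpha 0.04 and 0.017. The partial R² of duration, given the covariates already in the model, is not in the documents, so it is an assumption shown as a range. The SD of 1.2 is used as the residual SD of the planned model.

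**Plan's own FAS figure.** SE = 1.2 × √(1/34 + 1/17) = 0.356, and 1.2/0.356 = 3.367. The normal formula gives Φ(3.367 − 2.054) = 90.5%. A two-sample t test (49 df) gives 89.2%. The stated minimum of 85% is met.

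**FAS with and without duration.** The planned ANCOVA estimates five parameters (intercept, treatment, baseline, two factors), leaving 51 − 5 = 46 df. Adding duration leaves 45. The residual SD becomes 1.2 × √(1 − R²). Power is from the noncentral t distribution; the half-widths use the 95% t quantile.

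| Model | Assumed partial R² | Noncentrality | Power, 1.2 log | 95% CI half-width (log10) | Narrowing, 1 − √(1 − R²) |
|---|---|---|---|---|---|
| Planned, 46 df | – | 3.367 | 89.15% | 0.718 | – |
| Plus duration, 45 df | 0 | 3.367 | 89.12% | 0.718 | 0% |
| Plus duration | 0.05 | 3.454 | 90.6% | 0.700 | 2.5% |
| Plus duration | 0.10 | 3.549 | 92.1% | 0.681 | 5.1% |
| Plus duration | 0.15 | 3.651 | 93.5% | 0.662 | 7.8% |

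The lost degree of freedom is repaid at a partial R² of about 0.001.

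**Chance imbalance in the FAS.** The SE of the between-arm difference in mean duration is √(1/34 + 1/17) = 0.297 SD, so the 95% range is ±0.58 SD. With 26 of 51 subjects at or below the median and 17 on placebo, the hypergeometric probability that the arms differ by at least 20 percentage points in the short-duration share is 23.7%. The shift in the unadjusted estimate from a 1-SE imbalance is √R² × 1.2 × 0.297. At R² = 0.10 that is 0.11 log, and 0.22 log at 1.96 SE. At R² = 0 it is zero.

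**Subgroup.** With the same method (17 vs 9, 1.5 log, alpha 0.017), the planned model has 21 df and 66.9% power. Adding duration gives 66.6% at R² = 0, a loss of about 0.4 points, and 69.2% at R² = 0.05. Break-even is at R² of about 0.007. Cutting at the median also shrinks R². As an illustration, assume durations spread evenly over the whole days 1 to 7, with variance 4.0, and a subgroup of days 1 to 4, with variance 1.25, a ratio of 0.31. A FAS R² of 0.10 then becomes 0.031/(0.031 + 0.90) = 0.034, which gives about 68.3% power. (The 85% subgroup power stated in SAP 1.3 does not reproduce: 74.1% by the normal formula, 67.9% by t. That is a separate matter and does not depend on this covariate.)

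**Type I error.** At the SAP Appendix 2 boundaries of 2.054 and 2.379, a correlation of √0.5 gives an overall error of 0.04996. If the short/long split explained 10% of the variance and was left unadjusted, the correlation would be about √(0.5 × 0.9) = √0.45 and the error about 0.0508.

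**The case against.** The strongest reply is that no harm has been shown. Nothing in the documents links duration to DAVG7, and every R² above is assumed. The endpoint already subtracts baseline viral load and the model adjusts for it, so much of what time since onset says about the level of virus is already used. Only what it says about later change remains. Eligibility narrows its range further ("respiratory symptoms ≤ 7 days prior to IMP administration on Day 1/Baseline"), and dating an acute worsening of a chronic symptom is imprecise. The SD of 1.2 is stated for DAVG7 in the placebo group, not as an ANCOVA residual. If baseline and strata explained 20% of the variance (assumed), planned FAS power would be about 95%, and duration at R² of 0.05 to 0.10 would add 1 to 2 points.

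All of this stands, and it limits the size of the point. It does not remove it, because the cost in the FAS is close to zero even when duration explains nothing.

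A reader might infer that building a co-primary population on duration shows that the sponsor regards it as prognostic. The planning figures (1.5 log in the subgroup, 1.2 log overall, the same SD) imply a larger expected treatment effect in early presenters. That is a predictive role, and a main-effect covariate does not address it.

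A reader might also cite SAP Appendix 2, which sets the alpha split "assuming no prognostic or predictive effect of duration of RSV symptoms prior to the first dose on the primary endpoint", as evidence of harm. That is a working assumption for a correlation under the null, and departing from it moves the overall error only to about 0.051.

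**Conclusion.** The omission is real. The planned analysis remains valid: randomization keeps the estimate unbiased on average, the standard error already allows for chance imbalance, and the stated FAS power is met. The documents do not support saying that the plan certainly loses precision or that its estimate is biased. They support a conditional statement. If duration predicts DAVG7 beyond baseline viral load, the FAS test gives up about 1.5 to 4.3 percentage points of power at the planned 1.2 log difference (assumed partial R² 0.05 to 0.15) and 2.5% to 8% of interval width. It also has no pre-specified adjustment for an imbalance that could move the estimate by 0.1 to 0.2 log at R² = 0.10. If duration predicts nothing, including it costs about 0.03 points. That asymmetry justifies adding it for H01. For H02 the gain is small and the cost of a useless term is larger, about 0.4 points, so the case there does not extend to the primary model.

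**What to change.** In Protocol 8.5.1 and SAP 6.1.2, add duration of symptoms before first dose (days, continuous) as a covariate in the H01 ANCOVA. Leave the H02 primary model as planned, and list the duration-adjusted H02 model among the sensitivity analyses in SAP 6.1.3. If the FAS model is to stay as it is, state the reason and name the adjusted FAS model as a sensitivity analysis.

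The change must be fixed before unblinding. The plan's own sequence allows this: the SAP is finalized before the database (SAP 1), and the blind is broken only after the main-study data are final (SAP 2.2). The cost is one model term and one degree of freedom, from data already collected.

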### **6.1.3. Sensitivity Analysis for Primary Efficacy Endpoints**

The following sensitivity analyses will be performed:

- The primary endpoint time-weighted average change in nasal RSV viral load from Baseline to Day 7 will be analyzed in the PP analysis set.
- The primary endpoint time-weighted average change in nasal RSV viral load from Baseline to Day 7 will be analyzed for subjects in FAS who have at least one postbaseline nasal swab sample through Day 7.

